Sample Size	
See page 27-28 for more detailed calculations.
 
N = 120.
 
For the primary outcome, sample size calculation was based on the minimal clinically important difference in the ASES-score, and on data from a recently published, large prospective study from our research group. Following these assumptions, 60 participants are needed in each group to detect a clinically meaningful change in ASES scores with 80% power and a significance level of 0.05, after adjusting for a 10% dropout rate and the possible need for non-parametric tests.
 
An additional sample size calculation was made for the secondary outcome of change in PCS score from baseline between the control and intervention group, using the proposed minimal clinically important difference in the PCS score, with pooled data from the PCS development/validation studies and a French cohort of patients with RA to estimate the population distribution. Aiming to exclude any (negative) effect of the intervention on change in the PCS score, we chose a non-inferiority design for this outcome. Given that the effect of the intervention on the PCS score is unknown, we chose the aforementioned minimal clinically important difference as the non-inferiority margin. Following these assumptions and allowing for a 10% dropout rate, a total of 82 participants need to be included (41 in both the control and intervention groups) to demonstrate a non-inferior effect of the intervention on the PCS score with 80%

	
power, a minimal clinically important margin and a two-sided significance level of 0.025. When 120 patients are included as per the primary outcome, and assuming a 10% drop-out rate, we should have 90.2% power to demonstrate non-inferiority for this secondary outcome.
 
In summary, a total of 120 patients will need to be included to assess both the primary outcome of self-efficacy and the secondary outcome of pain catastrophizing with at least 80% power, with 60 participants in both the control group and the intervention group.

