9.1 Sample size

For the primary outcome, we opted for a superiority design aiming to reject the null hypothesis that there would be no difference between the intervention and control groups in the change of the total ASES-score from baseline to week 16. Sample size calculation was based on the previously proposed minimal clinically important difference in the ASES-score, corresponding with a change of 5.5 on either the pain or other symptoms subscale (13,25). Moreover, in a recently published, large prospective study from our research group, including 379 patients with RA, the mean (\pm SD) self-efficacy for pain (PSE) was 31.8 (\pm 8.9) and self-efficacy for other symptoms (OSE) was 42.6 (\pm 9.4) (32). Based on a minimal clinically important difference of 5.5 and population SD of 9.4, an effect size of approximately 0.59 was assumed. Additionally, based on previous research and outpatient clinic attendance experience, we expect dropout rate to be maximally 10% (13,24,33). Following these assumptions and in the setting of a superiority trial, 52 participants are needed in each group to detect a clinically meaningful difference in either PSE or OSE with 80% power and a significance level

of 0.05, while allowing for a 10% dropout rate.

It should be noted that the ASES score was not fully normally distributed in our aforementioned prospective study, implying that non-parametric tests might be needed to analyze the primary outcome. Following a general rule of thumb, sample size was thus increased by 15% to account for the loss of power these non-parametric tests would imply(34). Consequently, a total of 120 participants are needed (60 in each group) for the analysis of the primary outcome, with 80% power and a significance level of 0.05.

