An additional sample size calculation was conducted for the secondary outcome of change in PCS score from baseline in the intervention group compared to the control group. Based on pooled data from the PCS development/validation studies and a French cohort of patients with RA, the population weighted mean (SD) PCS score is estimated at 20.3 (SD 12.3) (27,35,36). Thus, a clinically important difference in the PCS score, previously proposed as greater than 38% change (27,37), would correspond to a change in total PCS score of greater than 7.7/52. Aiming to exclude any (negative) effect of the intervention on change in the PCS score, we chose a non-inferiority design for this outcome. Given that the effect of the intervention on the PCS score is unknown, we chose the aforementioned minimal clinically important difference of 7.7 as the non-inferiority margin. In other words, non-inferiority will be confirmed if the upper bound of the 95% CI for the intervention's effect on PCS remains within a minimal clinically important margin(38). Following these assumptions and allowing for a 10% dropout rate, a total of 82 participants need to be included (41 in both the control and intervention groups) to demonstrate a non-inferior effect of the intervention on the PCS score with 80% power, a minimal clinically important margin and a two-sided significance level of 0.025. When 120 patients are included as per the primary outcome, and assuming a 10% drop-out rate, we should have 90.2% power to demonstrate non-inferiority for this secondary outcome.

Sample size calculations were conducted via R version 4.2.1, using the packages *pwr* and *epiR* (see Appendix B). In summary, a total of 120 patients will need to be included to assess both the primary outcome and the secondary outcome with at least 80% power, including 60 participants in both the control group and in the intervention group.

As described above, the intervention group will then again be randomized in a 1:1-ratio to assess the exploratory outcomes. The trial will thus not be powered for the exploratory analyses.

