9.2 Analysis

Analyses will be carried out according to the intention-to-treat (ITT) principle, implying that participants will be analyzed based on the group they were originally assigned to.

In this study, the ITT population will consist specifically of all patients in the intervention group who effectively downloaded and installed the Sidekick application at the baseline visit, and all patients assigned to the control group. As stated above, participants in the intervention group will be re-randomized to intervention arm A or B, constituting two additional ITT populations that will only be analyzed exploratorily.

Per protocol (PP) analyses will be carried out as sensitivity analyses, including only those patients who completed the follow-up visit.

The variables described above in sections 4-6 will be extracted from the electronic medical patient file that is employed in all participating centers (KWS). Additionally, user behavior statistics and data actively logged by the patients in the app will be collected and provided for analysis in pseudonymized form by Sidekick Health. The primary and secondary outcome data of this study will be collected via questionnaires on the MyNexuzHealth app, or if not possible in pen-and-paper format at the outpatient clinic. All study-related information will be assembled and prepared for further analysis in an electronic CRF developed in REDCap. P-values <0.05 will be considered as statistically significant for all analyses. Missing data will be handled with multiple imputation by chained equations when data can be assumed to be missing at random. Descriptive statistics for baseline participant characteristics will be provided as means (\pm SD), medians (IQR) or proportions depending on data distribution.

Primary endpoint

The difference in mean change of total ASES (Arthritis Self-Efficacy Scale) score from baseline to week 16 \pm 2w in the intervention group when compared to the control group will be evaluated with an unpaired t-test or Wilcoxon rank sum test depending on distribution of the ASES-score. As a sensitivity analysis, we will additionally assess the difference between groups in week 16 scores using ANOVA adjusted for the baseline score. Furthermore, differences in the pain and other symptoms subscales of the ASES will be presented separately.

Secondary endpoints

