# Accounting for 10% drop-out
samplesize <- power$n.total*1.10

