# Calculation of power with 120 participants and 10% drop-out (= 108):
power <- epi.ssninf(treat = 20.3, control = 20.3, sd = 12.3, delta = 7.7, n = 108, r = 1,
power = NA, alpha = 0.025)
```

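### The 82 participants stated for the PCS non-inferiority test is the figure before dropout, and its significance level is mislabelled as two-sided 0.025; N = 120 and the 90.2% power are unaffected

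*Combined protocol and SAP*

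**What the plan says.** Section 9.1 sizes the PCS comparison as a non-inferiority test with a margin of 7.7 points and an SD of 12.3. It states that, "allowing for a 10% dropout rate, a total of 82 participants need to be included", which is 41 per group. The same sentence gives 80% power, "a minimal clinically important margin and a two-sided significance level of 0.025". Earlier in that paragraph the decision rule is that "non-inferiority will be confirmed if the upper bound of the 95% CI" stays inside the margin. The paragraph ends with 90.2% power if 120 are enrolled and 10% drop out.

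The Sample Size entry of the synopsis repeats the 82, the dropout allowance, the two-sided 0.025 and the 90.2%, but not the confidence interval rule.

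Appendix B calls the non-inferiority function `epi.ssninf` with alpha 0.025 and power 0.80, and only then applies the dropout step, "samplesize <- power$n.total*1.10". A last call computes power at 108 evaluable participants.

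For the primary outcome (ASES), section 9.1 says that "52 participants are needed in each group to detect a clinically meaningful difference in either PSE or OSE with 80% power", again with the 10% dropout allowance included.

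**The concern.** There are two inconsistencies.

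First, the text presents 82 as a number to enrol with dropout already covered, whereas the script has a separate dropout step that comes after its sample size call. If 82 is the result before that step, the stated requirement is too low for its stated dropout and power.

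Second, a rule based on the upper limit of a two-sided 95% interval spends 0.025 in one tail. A two-sided level of 0.025 would spend 0.0125 in that tail and correspond to a 97.5% interval. The two descriptions cannot both define the test.

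PCS is the only secondary endpoint and carries the question of whether the app worsens pain perception. Section 9.2 names a t-test or Wilcoxon test for PCS but gives no margin, interval level or sidedness. Section 9.1 is therefore the only place in the text that defines the non-inferiority test.

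**Working it through.** **Inputs.** From section 9.1 and Appendix B: SD 12.3, margin 7.7, true difference 0 (20.3 in both groups), 1:1 allocation, power 0.80, alpha 0.025, dropout 10%. Normal quantiles: 1.960 (one-sided 0.025), 2.2414 (one-sided 0.0125), 0.8416 (power 0.80).

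**Reproducing the 82.**

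n per group = 2 × ((1.960 + 0.8416) × 12.3 / 7.7)² = 40.06, rounded up to 41, total 82.

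This matches the stated figure exactly, with no dropout included.

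**Adding dropout.**
- Script's method: 82 × 1.10 = 90.2.
- Dividing by the retained fraction: 82 / 0.90 = 91.1.
- Rounded up to equal groups, both give 92 (46 per group).

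The 90.2 participants and the 90.2% power agree only by coincidence; the power is computed separately below.

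**Could 82 be a post-dropout figure under another reading?**

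| Reading | Before dropout | After dropout |
|---|---|---|
| One-sided 0.025, group size rounded up | 82 | 90.2 to 91.1 |
| One-sided 0.025, unrounded total | 80.1 | 88.1 to 89.0 |
| One-sided 0.025, t-based | 84 | 92.4 to 93.3 |
| One-sided 0.05 | 64 | 70.4 to 71.1 |
| Literal two-sided 0.025 | 98 | 107.8 to 108.9 |

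None gives 82 after dropout. For 82 enrolled (about 74 evaluable) to give 80% power, the one-sided alpha would have to be about 0.032, a value the plan does not state.

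**The same wording for the primary outcome.** The t-test calculation for 5.5/9.4 gives 46.83 per group. The total rounds to 94; 94 × 1.10 = 103.4; half of that is 51.7, so 52 per group, as stated. The dropout step was therefore applied for ASES but not for PCS.

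**Power.** Power = Φ(7.7 / (12.3 × √(4/N)) − z), with N the evaluable total.

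| N evaluable | z = 1.960 | z = 2.2414 |
|---|---|---|
| 74 | 76.8% | 67.4% |
| 82 | 80.9% | 72.3% |
| 108 | 90.2% | 84.4% |

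The plan's 90.2% reproduces only with z = 1.960, that is, one-sided 0.025.

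**Effect of the label on a verdict.** At 108 evaluable the standard error is 12.3 × √(4/108) = 2.367. The 95% interval rule declares non-inferiority if the observed worsening is below 7.7 − 1.960 × 2.367 = 3.06 points. A literal two-sided 0.025 would require it to be below 7.7 − 2.2414 × 2.367 = 2.39 points. The two rules disagree only between those values.

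**The case against.** The strongest reply is that this is editorial. The 82 sizes nothing, because N = 120 comes from the primary outcome. The next sentence of section 9.1 handles dropout correctly (120 enrolled, 108 evaluable, 90.2%). The claim of at least 80% power for PCS survives even the literal label, at 84.4%. The 95% interval rule is explicit in the same paragraph, so a careful analyst would not be misled. All of this stands, and it limits the point to a correction of the text.

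Two narrower objections also have some force. The general rule in section 9.2, "P-values <0.05 will be considered as statistically significant for all analyses", states no sidedness, so it does not support either label. The case here rests on the interval rule and the script, which settle the label without it.

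The other concerns the corrected size. Plain rounding of 90.2 would give 90. With 10% dropout that leaves 81 evaluable and 80.4% power, so 90 also meets the power target. However, 90 does not preserve the 82 evaluable that the calculation returns; the smallest equal-group total that does is 92 (92 × 0.90 = 82.8).

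The objection does not rescue either statement. As a figure that allows for dropout, 82 is wrong, and the stated level contradicts the rule beside it. The synopsis carries the wrong label without the rule that would correct it.

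**Conclusion.** Both errors are confirmed. The PCS requirement is 82 evaluable participants, or 92 enrolled in equal groups with 10% dropout, so the stated enrolment figure is 10 too low. The level that produced both 82 and 90.2%, and that matches the 95% interval rule, is one-sided 0.025.

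The practical effect is small. N = 120 exceeds 92, and the 90.2% at 108 evaluable does not change. Provided the 95% interval rule is the one applied, the type I error is one-sided 0.025 as designed. A different conclusion could arise only if an analyst followed the label instead of the interval rule and the observed worsening lay between 2.39 and 3.06 points.

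These figures use the plan's normal approximation, a true difference of zero and an SD of 12.3. Section 9.1 gives that SD for the PCS score, not for change in the score. The 90.2% is therefore reproduced here on the stated input; this check does not establish that the input suits the change score.

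**What to change.** Make two corrections, each in section 9.1 and in the Sample Size entry of the synopsis:

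1. Give the PCS requirement as 82 evaluable participants (41 per group), corresponding to 92 enrolled (46 per group) with 10% dropout.
2. Describe the level as one-sided 0.025, assessed by the upper limit of the two-sided 95% confidence interval.

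The cost is a few words in two places. N = 120, the 90.2% power, the Appendix B script and the analysis all stay as they are.

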9.2 Analysis

Analyses will be carried out according to the intention-to-treat (ITT) principle, implying that participants will be analyzed based on the group they were originally assigned to.

In this study, the ITT population will consist specifically of all patients in the intervention group who effectively downloaded and installed the Sidekick application at the baseline visit, and all patients assigned to the control group. As stated above, participants in the intervention group will be re-randomized to intervention arm A or B, constituting two additional ITT populations that will only be analyzed exploratorily.

Per protocol (PP) analyses will be carried out as sensitivity analyses, including only those patients who completed the follow-up visit.

The variables described above in sections 4-6 will be extracted from the electronic medical patient file that is employed in all participating centers (KWS). Additionally, user behavior statistics and data actively logged by the patients in the app will be collected and provided for analysis in pseudonymized form by Sidekick Health. The primary and secondary outcome data of this study will be collected via questionnaires on the MyNexuzHealth app, or if not possible in pen-and-paper format at the outpatient clinic. All study-related information will be assembled and prepared for further analysis in an electronic CRF developed in REDCap. P-values <0.05 will be considered as statistically significant for all analyses. Missing data will be handled with multiple imputation by chained equations when data can be assumed to be missing at random. Descriptive statistics for baseline participant characteristics will be provided as means (\pm SD), medians (IQR) or proportions depending on data distribution.

Primary endpoint

The difference in mean change of total ASES (Arthritis Self-Efficacy Scale) score from baseline to week 16 \pm 2w in the intervention group when compared to the control group will be evaluated with an unpaired t-test or Wilcoxon rank sum test depending on distribution of the ASES-score. As a sensitivity analysis, we will additionally assess the difference between groups in week 16 scores using ANOVA adjusted for the baseline score. Furthermore, differences in the pain and other symptoms subscales of the ASES will be presented separately.

Secondary endpoints

- The difference in mean change of total PCS score from baseline to week 16 \pm 2w in the intervention group will be compared to that in the control group, using an unpaired t-test or Wilcoxon rank sum test depending on distribution of the PCS score. As a sensitivity analysis, we will additionally assess the difference between groups in week 16 scores using ANOVA adjusted for the baseline score.

Exploratory endpoints

- The difference in mean change of total ASES score from baseline to week 16 \pm 2w in the intervention arm with weekly RAID questionnaires will be compared to that in the intervention arm with monthly RAID questionnaires, using an unpaired t-test or Wilcoxon rank sum test depending on distribution of the ASES-score. As a sensitivity analysis, we will additionally assess the difference between groups in week 16 scores using ANOVA adjusted for the baseline score.

- The difference in mean change of total PCS score from baseline to week 16 \pm 2w in the intervention arm with weekly RAID questionnaires will be compared to that in the intervention arm with monthly RAID questionnaires, using an unpaired t-test or Wilcoxon rank sum test depending on distribution of

the PCS score. As a sensitivity analysis, we will additionally assess the difference between groups in week 16 scores using ANOVA adjusted for the baseline score.

- The difference in mean change of total IPAQ-S score from baseline to week 16 ± 2w in the intervention group when compared to the control group will be evaluated with an unpaired t-test or Wilcoxon rank sum test depending on distribution of the IPAQ-S score. As a sensitivity analysis, we will additionally assess the difference between groups in week 16 scores using ANOVA adjusted for the baseline score.
- The difference in mean change of total PSQI score from baseline to 16 ± 2w in the intervention group when compared to the control group will be evaluated with an unpaired t-test or Wilcoxon rank sum test depending on distribution of the PSQI score. As a sensitivity analysis, we will additionally assess the difference between groups in week 16 scores using ANOVA adjusted for the baseline score.
- Participant engagement with the app will be analyzed descriptively as 1) the proportion of RAID questionnaires with at least one completed item in the Sidekick app, compared to the total number of RAID questionnaires prompted by the app for each participant during the study period; and 2) several user behavior statistics as described elsewhere. Additionally, participant engagement will be compared between the weekly and monthly RAID groups with unpaired t-tests or Mann-Whitney-U tests depending on data distribution.
- Candidate predictors of a favorable effect of using the Sidekick app on self-efficacy, sleep and physical activity will be studied exploratively with (multiple) linear regression.
- The evolution over time of the RAID scores at baseline, provided in the app (intervention group only) and at week 16 ± 2w, and their association with other outcomes including ASES, IPAQ-S, PSQI and DAS28-CRP/SDAI scores, will be described with linear mixed effects regression models.
- The association of data actively logged in the app (step counts, exercise activities, sleep quality, stress level, and energy level) with (changes in) the validated outcome measures RAID, IPAQ-S, PSQI, ASES, and DAS28-CRP/SDAI collected at baseline and week 16 ± 2w will be reported as Spearman or Pearson correlation coefficients depending on data distribution.

10. Quality assurance

Data collection tools and source document identification:

Source data will be collected and recorded in the study participants' files/medical records. They will be kept on a secured location at all times. The collection and processing of source data (from subjects enrolled in this study) will be limited to those data that are necessary to fulfill the objectives

of the study. These data must be collected and processed with adequate precautions to ensure confidentiality and compliance with applicable data privacy protection laws and regulations. Appropriate technical and organizational measures to protect the data against unauthorized disclosures or access, accidental or unlawful destruction, or accidental loss or alteration must be put in place. Personnel whose responsibilities require access to personal data agree to keep the data confidential.

Documentation of source data is necessary for the evaluation and validation of clinical findings, observations and other activities during a clinical study. Source documentation serves to substantiate the integrity of study data, confirms observations that are recorded and confirms the existence of study participants. Furthermore, source documentation must be available for the following to confirm data collected in the e-CRF: subject identification, eligibility, and study identification; study discussion and date of informed consent; dates of visits; results of safety and efficacy parameters as required by the protocol and date of study completion and reason for withdrawal from the study, if applicable. Data collection is the responsibility of the clinical study staff at the site under the supervision of the investigator. The investigator will maintain complete and accurate documentation for the study. All source documents will be reviewed by the clinical team to ensure that they are accurate and complete.

As defined in section 1.52 of the ICH Guideline for Good Clinical Practice (ICH E6) source documents may include: original documents, data and records (e.g., hospital records, clinical and office charts, laboratory notes....).

11. Direct access to source data and documents

The investigator will permit trial-related audits, IEC review and regulatory inspection, providing direct access to all related source data / documents.

E-CRF's and all source documents, including progress notes and copies of laboratory and medical test results must be available at all times for review by the data manager, auditor and inspection by health authorities (e.g. EMA, FDA). The accuracy of the data will be verified by review of the source documents sponsor's clinical trial monitor.

12. Ethics and regulatory approvals

The trial will be conducted in compliance with the principles of the Declaration of Helsinki (current version), the principles of GCP and in accordance with all applicable regulatory requirements. This protocol and related documents will be submitted for review to Ethics Committee and to the Federal Agency for medicinal products for Clinical Trial Authorization.

The Study can and will be conducted only on the basis of prior informed consent by the Subjects, or their legal representatives, to participate in the Study. The Participating Site shall obtain a signed

informed consent form (ICF) for all patients prior to their enrollment and participation in the Study in compliance with all applicable laws, regulations and the approval of the (local) Ethics Committee, if required. The Participating Site shall retain such ICFs in accordance with the requirements of all applicable regulatory agencies and laws. The ICF for this study includes a dedicated section to inform participants that they will be presented with general Terms and Conditions upon downloading the application.

The Investigator and the Participating Site shall treat all information and data relating to the Study disclosed to Participating Site and/or Investigator in this Study as confidential and shall not disclose such information to any third parties or use such information for any purpose other than the performance of the Study. The collection, processing and disclosure of personal data, such as patient health and medical information is subject to compliance with applicable personal data protection and the processing of personal data (Regulation (EU) 2016/679 also referred as the General Data Protection Regulation ("GDPR") and the Belgian Law of July 30 2018 on the protection of natural persons with regard to the processing of personal data).

Any personal data shall be treated as confidential at all times including during collection, handling and use, and that the personal data (including in any electronic format) shall be stored securely at all times and with all technical and organizational security measures that would be necessary for compliance with data protection legislation. The Sponsor shall take appropriate measures to ensure the security of all personal data and guard against unauthorized access to or disclosure of or loss or destruction while in its custody.

The personal data of study participants will be encoded, which means that they can only be related to an identifiable person by means of a unique code. The unique code will only be in the possession of the members of the study team who are in direct contact with the study participants. In no event will the coded personal data include personal identifiers, including any Study participant's initials. Such coded personal data can only be traced or linked back by said study team members and said study team members shall treat these codes as strictly confidential.

13. Data Handling

Data collection tools and source document identification

The Terms and Conditions in the informed consent form (ICF) also apply to the storage and handling of personal data, specifically account registration information, user-logged data and user behavior data.

According to these general Terms and Conditions, account registration information, data logged by users in the SidekickHealth application, and user behavior data are stored in the Google Cloud SQL service on behalf of GoodlifeMe, the SidekickHealth manufacturer. Google does not have access to this information for any other reason than to store it. Account registration information includes a user's name, email and chosen password, as well as information about their height, weight, age,

gender and profile picture if app users choose to supply this. To protect the personal email address of the user, we will label the individual patient account with a unique code (coded study email address) that will also serve as the study identification code for that individual in the eCRF. This code will be matched with the unique patient identification number in the KWS (EAD number) and kept in a separate file only available to the local study team. Logged data includes only the information actively logged by the user relating to their diet, physical activity, stress (such as minutes spent completing relaxation exercises in the application), vital signs, and questionnaires entered into the application. User behavior data include specific information about how participants use the application, such as how often the app is used, to what extent the educational modules have been accessed, how often certain lifestyle information is uploaded, to what extent patients have used a wearable together with the app etc... Upon deletion of the Sidekick account, or when the user has not logged any activity in the application for a period of two years, all personally identifiable data is deleted from the Google Cloud SQL service.

Other than user behavior data and actively logged data, no data derived by or entered into the Sidekick application will be collected or stored as part of this study. Demographic, clinical and questionnaire-derived source data will be collected and recorded in the study participants' files/medical records. They will be kept on a secured location at all times. The collection and processing of source data (from subjects enrolled in this study) will be limited to those data that are necessary to fulfill the objectives of the study. These data will be collected and processed with adequate precautions to ensure confidentiality and compliance with applicable data privacy protection laws and regulations. Appropriate technical and organizational measures to protect the data against unauthorized disclosures or access, accidental or unlawful destruction, or accidental loss or alteration will be put in place. Personnel whose responsibilities require access to personal data agree to keep the data confidential.

Documentation of source data is necessary for the evaluation and validation of clinical findings, observations and other activities during a clinical study. Source documentation serves to substantiate the integrity of study data, confirms observations that are recorded and confirms the existence of study participants. Furthermore, source documentation will be available for the following to confirm data collected in the e-CRF: subject identification, eligibility, and study identification; study discussion and date of informed consent; dates of visits; and date of study completion and reason for early discontinuation of study or withdrawal from the study, if applicable. Data collection is the responsibility of the clinical study staff at the site under the supervision of the investigator. The investigator will maintain complete and accurate documentation for the study. All source documents will be reviewed by the clinical team to ensure that they are accurate and complete. As defined in section 1.52 of the ICH Guideline for Good Clinical Practice (ICH E6) source documents may include: original documents, data and records (e.g., hospital records, clinical and office charts, laboratory notes....).

Case report forms

CRFs are provided for each subject in electronic format. The study data will be transcribed on a regular basis by study personnel from the source documents onto an e-CRF in a pseudo-anonymized manner and transmitted in a secure manner to the Chief Investigator within the timeframe agreed upon between Chief Investigator and the sites.

Worksheets may be used for the capture of some data to facilitate completion of the e-CRF. Any such worksheets (including but not limited to copies of the e-CRF) will become part of the study participant's source documentation. All data relating to the study must be recorded in e-CRFs prepared by the investigator. Data must be entered into e-CRFs in English. Designated site personnel must complete the e-CRF as soon as possible after a subject visit, and the forms should be available for review.

The investigator will ensure that data are recorded on the e-CRFs as specified in the study protocol and in accordance with the instructions provided.

All e-CRF entries, corrections, and alterations must be made by the investigator or other authorized study-site personnel. Proper audit trails are available to demonstrate the validity of the trial data. A copy of the completed e-CRFs will be archived at the study site.

Data handling and record keeping

The investigator will maintain a certified copy of e-CRFs and all source documents that support the data collected from each study participant, as well as all study documents as specified in ICH/GCP Section 8, Essential Documents for the Conduct of a Clinical Trial, and all study documents as specified by the applicable regulatory requirement(s). The investigator will take measures to prevent accidental or premature destruction of these documents.

If data need to be transferred, this will be performed via a secured method of transfer taking into account all applicable security arrangements and regulations. Receiving party will agree to keep the transferred data confidential at all times. Data will not be transferred outside of the EEA.

14. Data Management

The investigator will maintain a certified copy of e-CRFs and all source documents that support the data collected from each study participant, as well as all study documents as specified in ICH/GCP Section 8, Essential Documents for the Conduct of a Clinical Trial, and all study documents as specified by the applicable regulatory requirement(s). The investigator will take measures to prevent accidental or premature destruction of these documents.

If data need to be transferred, this will be performed via a secured method of transfer taking into account all applicable security arrangements and regulations. Receiving party will agree to keep the transferred data confidential at all times. Data will not be transferred outside of the EEA.

The Sponsor is responsible for archiving study-specific documentation (such as but not limited to protocol, potential amendments, final report and database) according to ICH-GCP. Source data and Site-specific study documents (such as, but not limited to, ICF) will be archived locally on site according to local practice and guidelines for at least 20 years. Archived data may be held on electronic record,

provided that a backup exists and that hard copies can be obtained, if required. Destruction of essential documents will require authorization from the Sponsor.

Archiving at the end of the trial will be organized by the sponsor and done centrally.

15. Translational research

No biological material will be collected/shipped/stored/used for the study. Lab results obtained as part of routine care will be extracted from the electronic medical patient file (KWS) or via laboratory reports of the participants' general practitioner.

16. Publication Policy

It is anticipated that the results of the overall Study shall be published in a multi-center publication, involving the data of all clinical sites participating in the Study.

Sponsor shall have the right to delay the projected publication for a period of up to three (3) months from the date of first submission to the Sponsor in order to enable the Sponsor to take steps to protect its intellectual property rights and know-how.

Publications will be coordinated by the Investigator of Sponsor. Authorship to publications will be determined in accordance with the requirements published by the International Committee of Medical Journal Editors and in accordance with the requirements of the respective medical journal.

17. Insurance/Indemnity

